10.2 Per Protocol Population

The PP Population is a subset of FAS and includes all randomized subjects who:

- Have no major protocol deviation to product compliance as defined in **Table 14** if randomized to THS 2.2 or SA.
- Have not been misrandomized.
- Have no other major protocol deviation.*

*Only subjects with major protocol deviations that impact the validity of the evaluation of the results (see Section 11 “Protocol Deviations”) will be excluded in the PP Population.

10.3 Safety Population

The Safety Population consists of all the subjects who had at least one exposure to THS 2.2 (product test at Admission Day). Subjects in the Safety Population will be analyzed according to actual exposure.

11 PROTOCOL DEVIATIONS

Protocol deviations are defined as those deviations from any procedure as defined in the Study Protocol, including but not limited to, as any violation of inclusion/exclusion criteria, mis-randomizations, use of any nicotine or tobacco-containing product other than the assigned product during each of the exposure period, assessments not performed or performed outside the scheduled time windows, or drugs that are known to affect CYP2A6 activity.

Information following site monitoring and other reviews will be documented in the site visit reports, follow-up letters, audit documentation, or other manual review and subsequently recorded in an electronic data capture (EDC) system. Additional protocol deviations may be identified in the data, these will also be recorded in the EDC system.

All deviations will be reviewed to determine their severity/impact when subjects are assigned to analysis populations. Each deviation will be classified as major or minor; all major deviations will be further reviewed to determine whether or not the deviation impacts the evaluability of the results and therefore should result in the subject being excluded from the PP Population.

11.1 Major Protocol Deviations

Subjects with major protocol deviations will be identified (at a population level) to determine whether they will be excluded from any analysis population. This will take place during the pre-analysis data review meeting prior to database lock. The following have been identified as the major protocol deviations.

The categories for the major deviations will include, but are not limited to the deviations presented in Table 14.

Table 14: Definition of Major Protocol Deviations

Category	Description
Mis-randomization	Being administered the wrong product according to the randomization schedule.
	Use of any nicotine or tobacco-containing product other than the assigned product.
Product compliance	Exhaled CO breath test >10 ppm for subjects from the SA arm after Day 2
Violation	Violation of inclusion/exclusion criteria.
Duration of 24 hour collection	Start and end times not within the 30 min window.

Among the above criteria, violations of inclusion criteria 5 to 7, or of the exclusion criteria 1, 3 to 16, and 18 will be assessed for their impact on the PP Population and evaluated during the pre-analysis data review meeting (Section 6.3.1 “Methods of Assigning Subjects to Product Arms”).

11.2 Minor Protocol Deviations

The categories for the minor deviations will include, but are not limited to the deviations presented in Table 15.

Table 15: Definition of Minor Protocol Deviation Categories

Category	Description
Concomitant medication	Use of drugs which are known to affect CYP2A6 activity.
Time deviation (Questionnaires)	Assessments not taken at the correct time or within the allowed time window (see Table 16 Error! Reference source not found.)
Time deviation (Blood draws)	Assessments not taken at the correct time or within the allowed time window (see Table 16)
Time deviation (CYP1A2 activity)	Assessments not taken at the correct time or within the allowed time window (see Table 16)
Time deviation (CYP2A6 activity)	Assessments not taken at the correct time or within the allowed time window (see Table 16)
Time deviation (Assessment of cough)	Assessments not taken at the correct time or within the allowed time window (see Table 16)
Time deviation (CO breath test)	Assessments not taken at the correct time or within the allowed time window (see Table 16)
Time deviation (HST Recording)	Assessments not taken at the correct time or within the allowed time window (see Table 16)
Time missing	Assessment date or time is missing
Assessment missing	Assessment is missing
Visit missing	Scheduled visit not done

11.3 Assessment Windows

Smoking of the randomized products should take place within the 06:30 AM and 11:00 PM window.

The assessment windows are shown in Table 16.

Table 16: Assessment Windows

Assessment	Nominal Time point(s)	Window
24 h urine sample	Start (All days)	06:30 AM ± 30 min
	End on the following day (All days)	06:29 AM ± 30 min
CYP1A2 activity in plasma	Start (Days 0 and 5)	6 hours after intake of cup of coffee ± 15 min
CYP2A6 activity	Day 0 and Day 6	Prior to smoking / product use

**Table 16: Assessment Windows**

Assessment	Nominal Time point(s)	Window
CO breath test	Day -2 and Day 6	Irrespective of product use
	Morning (Days -1 to 5)	To be done within 15 minutes prior to product use (for THS 2.2 and CC arms) or between 08:00 AM and 09:30 AM (SA arm)
	Day -1 to Day 5	Between 12:00 PM, 02:00 PM, 04:00 PM and 06:00 PM, and 08:00 PM and 10:00 PM
Assessment of Cough	Day 0 to 6	To be done prior to product use but not later than 10:00 PM.
MNWS questionnaire	Day 0 to 6	To be done prior to product use but not later than 10:00 PM
QSU-brief questionnaire	Day -1 to 5	08:00 PM to 11:00 PM
MCEQ questionnaire	Day -1 to 5	08:00 PM to 11:00 PM
Nicotine and cotinine in plasma	Day 0 to Day 4 between 08:00 PM and 10:00 PM Day 5 for THS 2.2 and CC arms: within 15 minutes before first product use (T_0): then additional blood samples at 2 hour intervals from T_0 until 11:00 PM. Day 6: 20 and 24 h after T_0 of Day 5	Each sample has a 5 minute time window 5 minute time window
COHb blood sampling	Days -1 to 4	8:00 PM to 11:00 PM
	Morning sample on Day 5	Within 15 minutes prior to product use (for THS 2.2 and CC arms) or between 08:00 AM and 09:30 AM (SA arm)
	Day 5 other samples	Between 12:00 PM and 02:00 PM, 04:00 PM and 06:00 PM, and 08:00 PM and 10:00 PM
HST Questionnaire	Day 0	08:00 PM-11:00 PM
	Day 4 for all subjects in the THS 2.2 and CC arms	08:00 PM-11:00 PM
HST Recording	Day 0	06:30 AM-11:00 PM
	Day 4 for all subjects in the THS 2.2 and CC arms smoking compatible CC	06:30 AM-11:00 PM

12 Planned Statistical Methods

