7.5.1 Biomarker of Exposure

7.5.1.1 Exhaled CO and Carboxyhemoglobin

Carboxyhemoglobin measured in blood and exhaled CO will be investigated as a measure of CO in all 3 study arms. The CO breath test should be conducted in timely conjunction with

the blood sampling for COHb, where applicable. In the SA arm, the CO breath test will serve as a verification of compliance (see Section 6.5.4).

Carbon Monoxide Breath Test

Carbon monoxide in exhaled breath will be measured using the Smokerlyzer[®] e.g. Micro+[™] Smokerlyzer[®] or similar device.

On Days -1 to Day 5, the CO breath test will be conducted 4 times per day. The first test should be conducted within 15 minutes prior to the first product use. The other 3 tests should be conducted as defined in section 9.

On Days 1 to Day 5, for subjects in the SA arm, the first CO breath test will be done between 08:00 AM and 10:00 AM. The other 3 tests should be conducted as defined in section 9.

On Day -2 and Day 6, the CO breath tests will be conducted once.

Carboxyhemoglobin

Assessment for COHb will be performed at the local laboratory. Carboxyhemoglobin in blood will be assessed on a daily basis, starting from Day -1 until Day 5.

On Day -1 to Day 4: one blood sample as defined in section 9.

On Day 5: one blood sample will be collected within 15 minutes prior to the first product use. The three other blood sample will be collected as defined in section 9.

For subjects in the SA arm, the first COHb will be done between 08:00 AM-10:00 AM. The three other blood samples will be collected as defined in section 9.

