9.2.2 Baseline Period (Day -1 to Day 0)

Table 8 and Table 9 show the assessments that will be performed at baseline (Day -1 and Day 0, respectively).

The start times given are for the first subject. All subsequent subjects should complete procedures within the time window given in the tables.

Table 8. Time Schedule - Day -1

| Time | Blood sample | Procedures | Additional information |
|-------------------------------|--------------|--|--|
| Start of procedure | | Baseline Day -1 | |
| | | AE/SAE recording; concomitant medication | All day |
| 06:30 AM+/- 30min | | Start urine collection to Day -1 sampling bottle | |
| | | CO breath test | To be done within 15 minutes prior to smoking |
| 06:30 AM | | Beginning of smoking period | |
| Before 10:00 AM | | Breakfast | |
| before 12:00 PM | | Vital signs (blood pressure, pulse rate, respiratory rate) | At least 5 minutes in supine position prior to measurement |
| 12:00 PM- 02:00 PM | | CO breath test | |
| before 03:00 PM | | Lunch | |
| 04:00 PM- 06:00 PM | | CO breath test | |
| Afternoon | | Snacks | |
| In the evening until 09:00 PM | | Dinner | |
| 08:00 PM- 10:00 PM | | CO breath test | |
| 08:00 PM- 10:00 PM | √ | COHb in blood | |
| 08:00 PM- 11:00 PM | | MCEQ questionnaire , QSU-brief questionnaire | |
| 11:00 PM | | End of smoking period | |

Confidentiality statement: Data and information contained in this document are considered to constitute trade secrets and confidential commercial information, and the legal protections provided to such trade secrets and confidential information are hereby claimed under the applicable provisions of applicable law. No part of this document may be publicly disclosed without the written consent of Philip Morris Products S.A.

06:30 AM-
11:15 PM

Collection of all smoked CC butts

For accountability

Abbreviations: AE = adverse event; CC = conventional cigarette(s); CO = carbon monoxide; COHb = carboxyhemoglobin; MCEQ = Modified Cigarette Evaluation Questionnaire; QSU-brief = Questionnaire of Smoking Urges (brief version); SAE= serious adverse event; THS 2.2 = Tobacco Heating System 2.2.

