g: On Days -1 to Day 5, the CO breath test will be conducted 4 times per day. For subject in the THS 2.2 and CC arms, the first test should be conducted prior to the first product use. The other 3 tests should be conducted as described in section 9 of the protocol.

On Days 1 to Day 5, the CO breath test will be conducted 4 times per day. for subjects in the SA arm, the first CO breath test will be done 08:00 AM-10:00 AM. The other three tests will be conducted as described in section 9 of the protocol.

On Day -2 and Day 6, the CO breath tests will be conducted once.

h: COHb; Assessments should be done in conjunction with CO breath tests, where applicable. Day -1 to Day 4: one blood sample in the evening as described in section 9 of the protocol.

Day 5: four blood samples will be collected 4 times per day. one blood sample prior to the first product use (for subjects in the THS 2.2 and CC arms) and 08:00-10:00 AM for subjects in the SA arm, and the three remaining samples as described in section 9 of the protocol.

Philip Morris Products S.A.

Protocol ZRHR-REXC-03-EU

Statistical Analysis Plan

Final v 2.0 / 27 May 2014

Confidential

Page 84 of 84

i: Nicotine/cotinine: Day 0 to Day 4 (all study arms): one blood sample 08:00 PM-10:00 PM.
Day 5 and Day 6 (THS 2.2 and CC arms): one sample within 15 minutes prior to the T0; eight blood samples after T0 each at 2 hour intervals. On Day 6, two blood samples will be drawn. The first sample will be 20 hours after T0 and the second blood sample will be 24 hours after T0 (with T0 being the time of the first product use on Day 5).
Day 5 and Day 6 (SA arm): on Day 5, one blood sample in the evening 08:00 PM-10:00 PM. On Day 6, one blood sample to be drawn 08:00 AM-10:00 AM.

j: QSU-brief: Daily, from Day -1 to Day 5.

k: MNWS daily from Day 0 to Day 6.

l: MCEQ: Day -1 to Day 5 on a daily basis.

m: On Day 0, HST and HST questionnaire will be done in all subjects smoking CC compatible with the HST SODIM® device. On Day 1 and Day 4, HST and HST questionnaire will be done in all subjects in the THS 2.2 and CC arms. Smoking topography with the HST SODIM® device will not be done in subjects smoking CC that are incompatible with the HST SODIM® device (e.g. slim CC). No HST assessments will be done in subjects in the SA arm.

n: Samples will only be taken if additional consent for BoExp bio-banking is given by the subject.

Table A2 Schedule for 24-hour Urine Collection Assessments

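### SAP Table 16 sets CO and COHb time windows that differ from the protocol, so the minor time-deviation counts would be wrong if the table is applied as written

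*SAP*

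**What the plan says.** Protocol section 7.5.1.1 sets the SA-arm morning times. For Days 1 to 5, "for subjects in the SA arm, the first CO breath test will be done between 08:00 AM and 10:00 AM". For the Day 5 blood sample, "For subjects in the SA arm, the first COHb will be done between 08:00 AM-10:00 AM". Evening COHb on Days -1 to 4 is set day by day in the time schedules of protocol section 9. The Day -1 entry reads "08:00 PM- 10:00 PM | √ | COHb in blood", and Days 0 to 4 carry the same two hours. The introduction to protocol section 9 adds that a measurement taken inside its window is accepted variability and not a deviation.

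The SAP appendix (16.1, note g) repeats the protocol's CO rule: "for subjects in the SA arm, the first CO breath test will be done 08:00 AM-10:00 AM". Note h gives the same hours for the SA Day 5 morning COHb and refers to protocol section 9 for the evening draws.

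SAP Table 16 differs. For SA morning CO, in a row labelled Days -1 to 5, and for the SA Day 5 morning COHb it gives "or between 08:00 AM and 09:30 AM (SA arm"). For COHb on Days -1 to 4 it gives "8:00 PM to 11:00 PM". Its Day 5 evening COHb window, 08:00-10:00 PM, agrees with the protocol.

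SAP Table 15 makes Table 16 operative: the category "Time deviation (CO breath test"), like the one for blood draws, is judged against Table 16. SAP 12.2 then summarizes deviations by actual exposure, category and sub-category in Table 15.2.1.3.

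**The concern.** A deviation summary should report departures from the protocol. A program written from Table 16 would err in two directions. In the morning it is stricter than the protocol, and only for the SA arm, so it would report compliant tests as deviations in that arm alone. In the evening it is looser, so a COHb draw that is late under the protocol would pass in any arm, including the Day 0 draw that serves as baseline for the primary COHb analysis. At stake is how accurately study conduct is described by arm. Because the morning limit also contradicts the SAP's own appendix, two programmers working from the same SAP could produce different counts.

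**Working it through.** The plan states no figure to reproduce. The check compares the windows and then counts the measurements exposed.

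**Windows side by side**

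| Measurement | Protocol | SAP Table 16 | SAP appendix 16.1 |
|---|---|---|---|
| SA first CO test, Days 1-5 | 08:00-10:00 AM | 08:00-09:30 AM | 08:00-10:00 AM |
| SA first COHb, Day 5 | 08:00-10:00 AM | 08:00-09:30 AM | 08:00-10:00 AM |
| First CO test, Days -1 and 0 | 15 minutes before smoking, all subjects | row labelled Days -1 to 5 includes the SA clock window | SA clock window on Days 1-5 only |
| Evening COHb, Days -1 to 4 | 08:00-10:00 PM | 08:00-11:00 PM | refers to protocol section 9 |
| Evening COHb, Day 5 | 08:00-10:00 PM | 08:00-10:00 PM | refers to protocol section 9 |

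**Morning, SA arm only.** Inputs: 40 SA subjects (protocol 4.1), CO on five days, one Day 5 morning COHb.
- Window lost: 120 - 90 = 30 minutes, or 30/120 = 25% of the protocol window.
- Exposed: 40 x 5 = 200 CO tests, plus 40 COHb draws, 240 in all. None in the THS 2.2 or CC arms.
- Let f be the share taken at 09:30-10:00 AM. The documents do not give f, so 5%, 10% and 25% are assumptions; 25% corresponds to an even spread over the two hours.
- False flags = 240 x f.
- SA subjects with at least one false CO flag: f if each subject keeps the same slot every day; 1 - (1 - f)^5 if days are independent.

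| f | False flags (CO + COHb) | Subjects flagged, same slot daily | Subjects flagged, independent days |
|---|---|---|---|
| 5% | 10 + 2 = 12 | 5% | 1 - 0.95^5 = 23% |
| 10% | 20 + 4 = 24 | 10% | 1 - 0.90^5 = 41% |
| 25% | 50 + 10 = 60 | 25% | 1 - 0.75^5 = 76% |

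**Row label.** On Days -1 and 0 every subject is still smoking. Randomization is on Day 0 and the arm is disclosed on Day 1, so an arm-specific clock window has no meaning on Day -1. A literal reading would touch at most 40 x 2 = 80 tests.

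**Evening, all arms.** Scheduled draws on the six days -1 to 4: 80 x 6 = 480 (THS 2.2), 40 x 6 = 240 (CC), 40 x 6 = 240 (SA), in total 960. This is the number of scheduled draws, not the number drawn late. If 2% to 10% were taken at 10:00-11:00 PM (an assumption), 960 x 0.02 = 19 to 960 x 0.10 = 96 late draws would pass the COHb row of Table 16, in proportion to arm size.

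**The case against.** The strongest reply is that nothing inferential depends on this, and that is right. Table 15 classes these timing departures as minor. SAP 10.2 and section 11 exclude subjects from the per-protocol population only for major deviations that affect the results, and Table 14 has no CO or COHb timing item. Section 11 does have all deviations reviewed when populations are assigned, and a reader might infer that wrong counts could change membership. The SAP gives no route for that once a deviation is classed as minor, and no SAP rule drops a CO or COHb value because of its clock time.

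A reader might also infer damage to the primary COHb analysis. A Day 0 draw at 10:30 PM still meets the SAP 12.1.4 baseline definition and is used either way, and the Day 5 evening window, which supplies the primary value, agrees in both documents.

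Table 16 is also not the only safeguard. SAP section 11 defines deviations against the protocol's procedures and records monitoring findings as well. The evening CO test, and on Days 0 to 4 the nicotine draw, keep their 10:00 PM limit in Table 16, and COHb is to be taken alongside the CO test. A late session would often be noticed through those rows; only Day -1 has no nicotine draw. It would therefore be wrong to say that 960 draws go unchecked.

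On the row label, SAP 12.6.2.1 and note g of the appendix already point away from an SA clock window on Days -1 and 0, so the 80 tests are a ceiling from a literal reading. Finally, SAP section 9 covers changes to the statistical analysis; that it does not mention the windows is not a separate fault.

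What survives is that the table which defines the time deviations is wrong as written.

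**Conclusion.** The point holds as an inconsistency in an operative rule, with limited consequences. Applied literally, Table 16 would count compliant SA morning measurements as deviations and would not flag evening COHb draws up to an hour past the protocol limit. On assumed shares of 5-25%, the morning error gives 12 to 60 false flags among 240 SA measurements. The share of SA subjects with at least one false CO flag is 5-25% if timing repeats daily and 23-76% if days are independent. The 76% should not be quoted alone: it needs both even spread and independence, and the documents support neither. Protocol section 9 describes subjects being handled in sequence after a first-subject time, which makes some day-to-day repetition plausible.

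Only the morning error differs by arm; the evening error applies to all three. The documents therefore show a risk of lopsided counts, not that the counts will be lopsided. The effect is confined to the minor-deviation entries in Table 15.2.1.3. The per-protocol population and the primary analysis are unchanged. This is a worthwhile correction, not a threat to the conclusions.

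**What to change.** Reconcile SAP Table 16 with the protocol:
- SA morning CO on Days 1-5 and SA Day 5 morning COHb: 08:00-10:00 AM.
- First CO test on Days -1 and 0: the 15 minutes before smoking, for all subjects.
- COHb on Days -1 to 4: 08:00-10:00 PM.

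If any difference is intended, state and justify it in the SAP and bring the appendix notes into line. The cost is three table entries and the matching lines of the deviation program, changed before database lock. No new data are needed.

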6.2.3.3 Smoking Abstinence Arm

Subjects randomized to the SA study arm will be instructed to abstain from smoking from Day 1, 06:30 AM onwards until Day 5, 11:00 PM. They will not be provided with medication supportive for smoking abstinence.

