**Table 9. Time Schedule - Day 0**

| Time | Blood sample | Procedures | Additional information |
|---------------------------|--------------|--|---|
| Start of procedure | | Baseline Day 0 | |
| | | AE/SAE recording; concomitant medication | All day |
| | | Randomization | At any time during the day after eligibility criteria have been met. Subjects are not to be informed of their assigned arm until Day 1. |
| 06:29 AM +/-30 min | | Analysis sample to be taken after final portion of urine has been added to Day -1 sampling bottle. | BoExp and creatinine in 24-hour urine |
| 06:30 AM +/-30 min | | Start of urine collection to Day 0 sampling bottle | |
| | | Assessment of cough (VAS) | To be done prior to smoking but no later than 10:00 PM |
| | | MNWS questionnaire | To be done prior to smoking but no later than 10:00 PM |
| | | Spirometry without short-acting bronchodilator | To be done prior to smoking |
| | √ | CYP2A6 activity in plasma | To be done prior to smoking |
| | | CO breath test | To be done within 15 minutes prior to smoking |
| | | HST | HST SODIM [®] device has to be used for all product uses if compatible CCs are smoked |
| 06:30 AM | | Beginning of smoking period | |
| | √ | Clinical laboratory parameters (hematology, clinical chemistry) | To be done after at least 8 hours of fasting |
| | √ | Bio-banking for BoExp/ risk markers in serum/plasma (if consent is obtained) | To be done after at least 8 hours of fasting |
| | √ | Bio-banking for transcriptomics (if consent is obtained) | To be done after at least 8 hours of fasting |
| | | Urine safety analysis | |
| Before 10:00 AM | | Breakfast | |

Confidentiality statement: Data and information contained in this document are considered to constitute trade secrets and confidential commercial information, and the legal protections provided to such trade secrets and confidential information are hereby claimed under the applicable provisions of applicable law. No part of this document may be publicly disclosed without the written consent of Philip Morris Products S.A.

| Time | Blood sample | Procedures | Additional information |
|-------------------------------|--------------|---|--|
| Start of procedure | | Baseline Day 0 | |
| 10:00 AM-12:00 PM | | Vital signs (blood pressure, pulse rate, respiratory rate) | At least 5 minutes in supine position prior to measurement |
| 10:00 AM-12:00 PM | | A cup of coffee containing approximately 150 mg of CAF | |

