| 08:00 PM-10:00 PM | √ | COHb in blood | |
| 08:00 PM-10:00 PM | √ | Nicotine, cotinine in plasma | |
| 08:00 PM-11:00 PM | | MCEQ questionnaire (THS 2.2 and CC arms only) QSU-brief questionnaire | |
| 11:00 PM | | End of product use | |
| 6:30 AM-11:15 PM | | Collection of all used Tobacco Sticks and smoked CC butts | For accountability |
| | | Collection of all tobacco plugs and filters from all used Tobacco Sticks in dedicated vials | For analysis of combustion occurrences and filter analysis |

Confidentiality statement: Data and information contained in this document are considered to constitute trade secrets and confidential commercial information, and the legal protections provided to such trade secrets and confidential information are hereby claimed under the applicable provisions of applicable law. No part of this document may be publicly disclosed without the written consent of Philip Morris Products S.A.

Abbreviations: 8-epi-PGF 2α = 8-epi-prostaglandine F 2α ; 11-DTX-B2 = 11-dehydro-thromboxane B2; AE = adverse event; BoExp = biomarkers of exposure; CC = conventional cigarette(s); CO = carbon monoxide; COHb = carboxyhemoglobin; HST = human smoking topography; MCEQ = Modified Cigarette Evaluation Questionnaire; MNWS = Minnesota Nicotine Withdrawal Scale (revised version); QSU-brief= Questionnaire of Smoking Urges (brief version); SA = smoking abstinence; SAE = serious adverse event; THS 2.2 = Tobacco Heating System 2.2; VAS = visual analogue scale.

Table 11 shows the assessments that will be performed on Day 2 of the confinement period:

Table 11. Time Schedule - Day 2

| Time | Blood sample | Procedures | Additional information |
|---------------------------|--------------|--|--|
| Start of procedure | | Day 2 | |
| | | AE/SAE recording; concomitant medication | All day |
| | | Support during smoking abstinence (SA arm only) if needed | All day |
| 6:29 AM +/-30 min | | Analysis sample to be taken after final portion of urine has been added to Day 1 sampling bottle. Must be prior to first product use of Day 2 | BoExp and creatinine in 24-hour urine |
| 6:30 AM +/-30 min | | Start collection to Day 2 sampling bottle | |
| | | MNWS questionnaire | To be done prior to product use but not later than 10:00 AM |
| | | Assessment of cough (VAS) | To be done prior to product use but not later than 10:00 AM |
| | | CO breath test | To be done within 15 minutes prior to first product use (for THS 2.2 and CC arms) or 08:00-10:00 AM (SA arm) |

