7.3.4 Minnesota Nicotine Withdrawal Scale (revised edition) Questionnaire

The MNWS (Hughes and Hatsukami 2008) is a 24 hour recall that will be completed by the subject him/herself daily on Day 0 to Day 6 prior to product use to reflect the previous days experience. Therefore although it is collected on Days 0 to 6 it will be reported as Days -1 to 5. Only the self-reported part of the MNWS will be used.

The self-reported part of the MNWS consists of the following 15 items which are rated over the last 24 hours on a scale of 0 to 4 (see Table 6). Higher scores indicate greater intensity on that scale.

The total scores will be derived by summing the individual item scores if all items are non-missing, otherwise the total score will be set to missing. The first total score calculated by summing the first 9 items is based on validated items, the second score is

based on 6 extra items which are thought to have an impact on withdrawal but have not been validated.

Table 6: Minnesota Nicotine Withdrawal Scale (Revised Edition) Questionnaire Scores

	Question	Total Score
1	Angry, irritable, frustrated.	1 and 2
2	Anxious, nervous.	1 and 2
3	Depressed mood, sad.	1 and 2
4	Desire or craving to smoke.	1 and 2
5	Difficulty concentrating.	1 and 2
6	Increased appetite, hungry, weight gain.	1 and 2
7	Insomnia, sleep problems, awakening at night.	1 and 2
8	Restless.	1 and 2
9	Impatient.	1 and 2
10	Constipation	2
11	Dizziness	2
12	Coughing	2
13	Dreaming or nightmares	2
14	Nausea	2
15	Sore throat	2

If the baseline score is 0, the percent change from baseline will be calculated using a value of 1 for the denominator.

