7.3.6 Cough Assessment

Subjects will be asked to assess the respiratory symptom 'cough' using a VAS, three Likert scale questions, and one open ended question on a daily basis during the confinement period (on Day 0 to Day 6) prior to start of product use/smoking and no later than 10:00 PM. Although the symptoms are assessed on Days 0 to 6 the data reflects the

subjects respiratory symptoms from the previous day (Days -1 to Day 5) and therefore will be reported as Days -1 to Day 5 .

Subjects will be asked if they have experienced a regular need to cough, e.g., whether they have coughed several times in the previous 24 hours prior to assessment. If the answer is 'yes', subjects will be asked to complete questionnaire.

The VAS will assess how bothersome cough is to the subject ranging from 'not bothering me at all' to 'extremely bothersome', and this will be given a numeric value between 0 and 100, measured on a 100 mm scale.

Subjects will also be asked to assess the intensity and frequency of cough and the amount of sputum production on Likert scales as presented in **Table 7 “ Cough Assessment Likert Scales”**.

Table 7 Cough Assessment Likert Scales

Question	Likert Scale
1 The intensity of cough	1 = very mild 2 = mild 3 = moderate 4 = severe 5 = very severe
2 The frequency of cough	1 = rarely 2 = sometimes 3 = fairly often 4 = often 5 = almost always
3 The amount of sputum production	0 = no sputum 1 = a moderate amount of sputum; 2 = a larger amount of sputum; 3 = a very large amount of sputum.

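### The SAP's 10:00 PM limit for the MNWS and cough forms conflicts with the protocol and could put late forms from abstinent subjects under the wrong day, chiefly the Day 1 form

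*SAP*

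**What the plan says.** **Completion window.** SAP Table 16 gives the MNWS and the cough assessment the same limit on Days 0 to 6: "To be done prior to product use but not later than 10:00 PM". SAP 7.3.6 repeats it for cough: "prior to start of product use/smoking and no later than 10:00 PM". In the protocol, Table 9 (Day 0) reads "To be done prior to smoking but no later than 10:00 PM", and Table 10 (Day 1) has the same evening limit tied to product use. From Table 11 (Day 2) onward the limit becomes "To be done prior to product use but not later than 10:00 AM". Table 15 (Day 6) keeps 10:00 AM but ties it to smoking.

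**Day label.** SAP 7.3.4 says that the MNWS "is a 24 hour recall that will be completed by the subject him/herself daily on Day 0 to Day 6 prior to product use", and adds: "Therefore although it is collected on Days 0 to 6 it will be reported as Days -1 to 5". SAP 7.3.6 applies the same shift to cough, which "therefore will be reported as Days -1 to Day 5". Neither section makes the shift depend on the time of completion.

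**SA arm.** Protocol 6.2.3.3: "Subjects randomized to the SA study arm will be instructed to abstain from smoking from Day 1, 06:30 AM onwards until Day 5, 11:00 PM". For the morning CO and COHb tests, SAP Table 16 gives SA subjects their own clock window, 08:00 to 09:30 AM. It gives them none for the MNWS or cough.

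**Use of the data.** SAP 12.6.3.1.3 compares THS 2.2 with CC and with SA on the MNWS, in a repeated-measures model with a product by time-point term. It takes as baseline the last assessment before 06:29 AM on Day 1. Cough is listed and summarized by day (SAP 12.6.4.5.6). SAP Table 15 defines time deviations for both forms by reference to Table 16.

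**The concern.** Reporting a 24-hour recall under the previous day is sound when the form is completed early in the morning. It becomes unsound as completion moves into the evening, because the recall then mostly covers the current day. In the THS 2.2 and CC arms the requirement to complete the form before product use will usually keep it early. In the SA arm that requirement has no content on Days 1 to 5, so the SAP leaves only 10:00 PM as a limit.

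At stake is the day-by-day picture of withdrawal and cough in the SA arm, and the THS 2.2 versus SA comparison of the MNWS over time. A mislabelled form would be counted as in window, and the problem could arise in essentially one arm.

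**Working it through.** The plan states no figure on this point, so there is none to reproduce. The check has two parts.

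**1. The windows side by side**

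| Form collected on | Reported as | Protocol limit | SAP limit | Does product use bound SA subjects? |
|---|---|---|---|---|
| Day 0 | Day -1 | 10:00 PM (Table 9) | 10:00 PM | Yes, all subjects still smoke |
| Day 1 | Day 0 | 10:00 PM (Table 10) | 10:00 PM | No |
| Days 2 to 5 | Days 1 to 4 | 10:00 AM (Tables 11 to 14) | 10:00 PM | No |
| Day 6 | Day 5 | 10:00 AM (Table 15) | 10:00 PM | Discharge is in the morning |

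The documents disagree on five of the seven days. The SA forms that could be late are those of Days 1 to 5. Only the Day 1 form may be completed in the evening under both documents.

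**2. How much of the recall lies in the reported day**

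Inputs: a 24-hour recall (SAP 7.3.4 and 7.3.6); reporting under the previous day; completion at clock time *t* hours on Day *d*; a day that starts at *b* hours. I take *b* = 6.5 (06:30 AM), the boundary both documents use for the baseline and exposure periods, with midnight (*b* = 0) as a variant.

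Hours of recall in Day *d* = *t* − *b*. Hours in the reported day (*d* − 1) = 24 − (*t* − *b*).

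| Completed at | Day starts at | Hours in reported day | Hours in Day *d* |
|---|---|---|---|
| 10:00 AM | 06:30 AM | 24 − 3.5 = 20.5 (85.4%) | 10 − 6.5 = 3.5 (14.6%) |
| 10:00 AM | midnight | 24 − 10 = 14 (58.3%) | 10 − 0 = 10 (41.7%) |
| 10:00 PM | 06:30 AM | 24 − 15.5 = 8.5 (35.4%) | 22 − 6.5 = 15.5 (64.6%) |
| 10:00 PM | midnight | 24 − 22 = 2 (8.3%) | 22 − 0 = 22 (91.7%) |

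The half-way point is *t* = *b* + 12, which is 6:30 PM on the study-day boundary and noon on the calendar-day boundary. Under a 10:00 AM limit, most of the recall lies in the reported day on either definition. At 10:00 PM it does not on either.

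**Day 1 in the SA arm.** Abstinence starts at 06:30 AM. A form completed at 10:00 PM follows 22 − 6.5 = 15.5 hours of it, yet is reported as Day 0, a smoking day.

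**The case against.** The strongest reply is that the SAP does not govern when the site collects forms. The protocol does, and it closes both forms at 10:00 AM on Days 2 to 6 in every arm. Even on Day 1, Table 10 places them among the early-morning procedures, and SAP 7.3.4 clearly has a morning form in mind. The 10:00 PM entries may be no more than AM/PM slips. This stands as a limit on scope: on Days 2 to 5 there is a conflict between documents, not a rule that generates late forms. It does not remove the Day 1 exposure, nor the fact that the SAP tests timing against the wider window.

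A reader might infer three stronger things that the documents do not support:

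- **That the THS 2.2 versus SA comparison is biased.** Nothing says how many SA forms would be late. With none, there is no bias. SAP section 9 also makes the comparison over all time points the main one for the MNWS, and that is less sensitive to a one-day label shift than the daily pattern.
- **That an evening Day 1 form becomes the MNWS baseline.** Read literally, SAP 12.6.3.1.3 rules it out, since it comes after 06:29 AM. What remains is an ambiguity: the form carries the Day 0 label but fails the baseline definition, and the SAP does not say which form is used instead.
- **That late forms can never be flagged.** SAP section 11 defines deviations against the protocol, and the Table 15 categories are not exhaustive, so a breach on Days 2 to 5 might still be recorded. However, Table 15 points to Table 16 for these windows, so a check built on it would miss the breach.

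**Conclusion.** The point holds as an inconsistency with a possible, unquantified effect. SAP Table 16 and SAP 7.3.6 disagree with the protocol on Days 2 to 6 without listing this as a change. Combined with the unconditional day shift, the 10:00 PM limit allows an SA form to be reported under a day that covers only 8.5 of its 24 recall hours (35%) on the study-day boundary, or 2 of 24 (8%) by calendar day. The 92% figure for the current day rests on a midnight boundary; on the documents' own 06:30 AM boundary it is 65%.

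The firm exposure is the Day 1 SA form. For Days 2 to 5 the risk is that protocol breaches go unflagged. The conclusion assumes that the SA arm has no first use to time the form by, and that the shift is applied as written. The MNWS is exploratory and cough is a safety measure. The primary endpoints are unaffected. It is worth correcting because the stated rule is wrong for a compliant evening form and the correction is nearly free.

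**What to change.** - Reconcile SAP 7.3.6 and Table 16 with protocol Tables 9 to 15 on one morning window. Include protocol Table 10, the only exposure-period table that itself allows 10:00 PM.
- Give SA subjects an explicit clock window for both forms, as Table 16 already does for CO and COHb.
- Flag forms completed after the window as time deviations.
- State which form is the MNWS baseline, and how a Day 1 form completed after 06:29 AM is treated.
- Handle late MNWS forms in a sensitivity analysis. Automatic exclusion would remove data almost only from the SA arm. Cough has no by-day model, so the flag is enough there.

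The cost is a few lines of text, one flag and one small exploratory analysis. The downside is a few more minor deviations on record.
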